7.1. Trial Design

7.1.1. Testing purposes

The purpose of the clinical trial is aiming at validating the safety and efficacy of completely degradable occluder system and occluder surgical intervention delivery devices manufactured

by Shanghai Shape Memory Alloy Co., Ltd, through the current clinical trial research.

7.1.2. Trial Method Selection and Their Rationale

The current trial applied perspective, multiple centered, randomized controlled non-inferiority clinical trial. It is evaluated of the safety and efficacy of completely degradable occluder system in clinical application, with the ventricular septal defect occluder manufactured by Shanghai Shape Memory Alloy Co., Ltd as the clinical trial control product. It is evaluated of the safety and efficacy of occluder surgical intervention delivery devices in clinical application, with the occluder intervention delivery devices manufactured by Shanghai Shape Memory Alloy Co., Ltd as the clinical trial control product. The primary endpoint index for evaluating occluder surgical intervention delivery devices is that it can be released when the occluder is delivered to the lesion location during operation; and the primary endpoint index for evaluating completely degradable occluder system is the success rate at month 6, which is evaluated for efficacy through ultrasonic cardiogram.

7.1.3. Measures for reduction and avoidance for deviation.

- 1) Before research initiation, the sponsor should carry out relevant training for researchers participated in the current research, and ensuring that the researchers sufficiently understand the research flow, and skillful in the operation of research instruments; during the course of research, the researchers should carry out operation strictly according to the operating methods and specification in the research protocol, and the clinical research monitor should do well of the quality control and monitoring work, and ensure that the researchers carry out operation and implementation strictly according to the research protocol. It is implemented of the measures mentioned above during the entire research procedures, to reduce the losses or operation errors;
- 2) It applied strict randomized trial design, to avoid the selection deviation in treatment. After the trial started, when the subjects meet the inclusion criteria for testing, the researchers shall log on to the central randomizing system for randomized grouping.

- 3) Subjects are screened for inclusion and exclusion strictly according to the clinical diagnostic criteria in trial protocol, to reduce the selection deviation;
- 4) Application of independent data management and statistical analysis shall be conducive to reduce the trial errors. When the clinical trial is completed, do well of data management and sorting work, when data issues shall arise, the data analyst shall carry out data check up through data questioning table, and avoid the record errors.

7.1.4. Medical devices used in trial and medical devices used in control

Testing Instrument: Completely degradable occluder system manufactured by Shanghai Shape Memory Alloy Co., Ltd.

Models and Specifications: ABFDQ-I-04, ABFDQ-I-05, ABFDQ-I-06, ABFDQ-I-07, ABFDQ-I-08, ABFDQ-I-09, ABFDQ-I-10, ABFDQ-I-12, ABFDQ-I-14, ABFDQ-I-16, ABFDQ-II-04, ABFDQ-II-05, ABFDQ-II-06, ABFDQ-II-07, ABFDQ-II-08, ABFDQ-II-09, ABFDQ-II-10, ABFDQ-II-12, ABFDQ-II-14, ABFDQ-II-16, ABFDQ-III-04, ABFDQ-III-05, ABFDQ-III-06, ABFDQ-III-07, ABFDQ-III-08, ABFDQ-III-09, ABFDQ-III-10, ABFDQ-III-12, ABFDQ-III-14, ABFDQ-III-16, ABFDQ-IV-04, ABFDQ-IV-05, ABFDQ-IV-06, ABFDQ-IV-07, ABFDQ-IV-08, ABFDQ-IV-09, ABFDQ-IV-10, ABFDQ-IV-12, ABFDQ-IV-14, ABFDQ-IV-16, ABFDQ-V04, ABFDQ-V05, ABFDQ-V06, ABFDQ-V07, ABFDQ-V08, ABFDQ-V09, ABFDQ-V10, ABFDQ-V12, ABFDQ-V14, ABFDQ-V16

Instrument in control: Ventricular septal defect occluder manufactured by Shanghai Shape Memory Alloy Co., Ltd.

SQFDQ-IIi 04、SQFDQ-IIi 05、SQFDQ-IIi 06、SQFDQ-IIi 07、SQFDQ-IIi 08、SQFDQ-IIi 09、SQFDQ-IIi 10、SQFDQ-IIi 12、SQFDQ-IIi 14、SQFDQ-IIi 16

Testing Instrument: Occluder surgical intervention delivery devices manufactured by Shanghai Shape Memory Alloy Co., Ltd.

Models and Specifications: 5F、6F、7F、8F、9F、10F、12F、14F

Control Instrument: Occluder intervention delivery devices manufactured by Shanghai Shape Memory Alloy Co., Ltd.

Models and Specifications:

Models	Specifications
Type I	5F、6F、7F、8F、9F、10F、12F、14F
Type II	5F、6F、7F、8F、9F、10F、12F、14F
Type III	5F、6F、7F、8F、9F、10F、12F、14F
Type IV	5F、6F、7F、8F、9F、10F、12F、14F

7.1.5. Selection of subjects

7.1.5.1. Inclusion Criteria

- (1) The subjects and (or) their legal guardians should know the nature of the current research, and consent to participate in the current clinical trial according to all the clauses of the current research. They must sign the informed consent approved by the ethics commission, and agree to receive the post-operative treatment protocol, and finish the follow up and relevant inspection required by the follow up, according to the follow up requirements.
- (2) Aged between one year and 60 years old, with body weight higher than 10kg, male or not pregnant women;
- (3) Effective shunt mouth for VSD is between 3mm and 14mm;
- (4) The upper margin of VSD is no less than a distance of 3mm from the right coronary valve of aorta, without aortic right coronary valve shedding into VSD and aortic regurgitation above moderate degree;

7.1.5.2. Exclusion Criteria

If there is any of the following condition, the current subjects should be excluded from the participation in the clinical trial:

- (1) Irreversible pulmonary blood vessel diseases; Severe pulmonary artery hypertension accompanied by shunts in double directions;
- (2) Hemorrhagic diseases or blood coagulation dysfunction already known (including thrombocytopenia resulted from heparin), with contraindications against platelet treatment, or possible of rejection for blood transfusion;
- (3) Septicemia or severe infections within one month before occlusion operation;
- (4) There exists thrombus in the location of occluder, and patients with venous thrombosis at the insertion point of the catheter;
- (5) Cardiac deformity patients survived with VSD;
- (6) Patients deemed by the researcher as inappropriate for the application of the current

product

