5.3. Test Scopes

The test scopes of completely degradable occluder system: The current product is applied in the treatment of ventricular septal defect in congenital cardiac diseases;

The occluder surgical intervention delivery devices are dedicated in the surgical intervention operation, and they are used in the delivery of various occluders manufactured by the company into the lesion location for release. It is applied in the occlusion treatment for the atrial septal defects, ventricular septal defects and patent ductus arteriosus.

6. Products Indications and Contraindications, and matters in need of attention.

Indications:

Completely degradable ventricular septal defect occluder is a type of percutaneous ventricular

septal defects closure devices through catheter, used in the ventricular septal defects with abnormality of hemodynamics or enlargement of left ventricular inner diameter.

Contraindications:

- 1). Patients with moderate to severe resistant type pulmonary arterial hypertension.
- 2). There exists thrombus in the cardiac cavity. There is hemorrhagic diseases, such as active ulceration.

Matters in need of Attentions:

- 1). The degradable occluder system and occluder surgical intervention delivery devices have already been sterilized before discharge.
- 2). The product is disposable product, forbidden for application after resterilization after opening.
- 3). If it is discovered of the opening, damages, leakage of packages or over the sterilization validity period, please do not use it.
- 4). The selection of occluder delivery sheath is crucial, such defects as unmatched between the sheath tube and the occluder, may result in the delivery and withdrawal difficulty, even result in the blood vessel injury.
- 5). The product is only limited to the application by the physician already receiving occlusion technique trainings.
- 6). It is necessary to prepare for the emergency conditions, and withdraw the thrombus devices that may severely influence the flowing property of blood.
- 7). For allergic patients with polyactic acid, and poly (p-dioxanone), they may have allergic reaction for the product.
- 8). The product is applicable for MRI.
- 9). In order to avoid the adverse outcome, please read the manual carefully before application, in particular, it must take heed of all precautions and matters in need of attention.

7. General Design

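### Section 6 contraindicates patients whom exclusion criteria (1) to (5) in section 7.1.5.2 do not exclude: clearly for thrombus, possibly for pulmonary hypertension

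*Combined protocol and SAP*

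**What the plan says.** Section 6, which describes the degradable occluder, lists two contraindications. The first is "Patients with moderate to severe resistant type pulmonary arterial hypertension". The second joins thrombus ("There exists thrombus in the cardiac cavity") with bleeding disease.

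Section 7.1.5.2 lists six exclusion criteria. Criterion (1) covers irreversible pulmonary vascular disease and "Severe pulmonary artery hypertension accompanied by shunts in double directions". Criterion (4) is "There exists thrombus in the location of occluder, and patients with venous thrombosis at the insertion point of the catheter". Criterion (6) leaves the rest to the investigator: "Patients deemed by the researcher as inappropriate for the application of the current" product. None of the six refers to section 6.

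Entry to the trial is tied to these criteria. Section 7.1.3, item 2, says that "when the subjects meet the inclusion criteria for testing, the researchers shall log on to the central randomizing system for randomized grouping". Section 7.1.5.4 admits a patient who satisfies the inclusion criteria and none of the exclusions. The screening column of the flow chart in section 7.2 has a row for inclusion and exclusion criteria and none for contraindications.

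**The concern.** A contraindication list and an exclusion list in one protocol should identify the same patients as unsuitable, or one should refer to the other. Here the exclusion list is narrower on at least one item, and it is the list that operates at enrolment.

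Patient safety is the main issue. The implantation in section 7.3.2 passes a needle, a guide wire, a sheath and the occluder into the heart, and the protocol itself names intracardiac thrombus as a contraindication to the product. Section 10.2 gives misunderstanding of indications and contraindications as one of two possible main causes of failure or poor results, so the protocol regards clarity here as important.

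Consistency between centres is the second issue. With four centres, a case that depends on judgement may be accepted at one site and refused at another. Section 8.2.2 relies on strict entry criteria to treat all 108 patients as a single disease category.

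**Working it through.** No figure in the plan bears on this point, so the check is a comparison of text.

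**Step 1: compare the lists item by item.**

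- *Thrombus.* Section 6 covers the cardiac cavity without restriction. Exclusion (4) covers the occluder location, plus venous thrombosis at the insertion point. A thrombus elsewhere in the heart falls under section 6 and outside exclusion (4). This is a clear gap.
- *Pulmonary hypertension.* Section 6 covers moderate to severe disease of resistant type and sets no condition on shunt direction. Exclusion (1) requires either irreversible vascular disease, or severe hypertension together with bidirectional shunting. Disease of resistant type that is moderate, or severe without bidirectional shunting, falls outside exclusion (1) unless it is judged irreversible. If resistant and irreversible mean the same thing, there is little or no gap. The text is a translation and does not settle this.
- *Bleeding.* Exclusion (2) covers known hemorrhagic disease and coagulation dysfunction, which largely matches section 6. No clear gap.

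**Step 2: follow one patient through entry.** Take a patient with an intracardiac thrombus away from the defect who is otherwise suitable.

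- Inclusion (1) to (4) concern consent, age and weight, shunt size, and the relation of the defect to the aortic valve. All can be met.
- Exclusions (1), (2), (3) and (5) concern pulmonary vascular disease, bleeding or coagulation, recent infection, and accompanying cardiac malformation. None applies.
- Exclusion (4) does not apply, because the thrombus is not at either named site.
- Exclusion (6) applies only if the investigator decides that it does.

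So the patient can pass sections 7.1.3 and 7.1.5.4 and be randomised. Allocation is 1:1, so there is an even chance of receiving the device that section 6 says is contraindicated. The protocol lists no contraindications for the control occluder.

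**Step 3: follow the same patient into the analysis sets.**

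- The rejection rule in section 7.1.5.3 reaches only patients in whom the test instrument was not used, so it does not remove an implanted test-arm patient.
- The Full Analysis Set (section 8.9) is everyone randomised in whom a research device was applied. The patient is in it.
- The per-protocol set (section 8.9) needs trial completion and no severe breach. Violations of the inclusion and exclusion criteria are given as examples and the list is left open; section 8.4 leaves severe breach to the judgement of the main investigators. The patient violates neither named example, so inclusion is possible but not settled.

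**Step 4: effect on planned figures.** Aligning the two lists changes none of the inputs in section 8.2.1 (98% success in both arms, 8% margin, one-sided 2.5%, 80% power, 10% dropout), so 54 per group stands.

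**The case against.** The strongest reply is that the two lists are cumulative. Nothing in the protocol permits implanting a patient listed in section 6. Exclusion (6) removes those unsuitable for the product, and a contraindicated patient is the obvious example. Section 7.3.3(6) requires use of the device as the protocol directs. Section 7.4 has the monitor check conformity with the protocol in general, and a deviation leads to a breach report. All of this stands, and a careful investigator would probably refuse such a patient. But exclusion (6) is discretionary and does not mention section 6, and a general compliance check cannot say which of two differing lists decides eligibility.

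Three stronger readings are tempting, and the documents do not support them.

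- *That such a patient certainly stays in the per-protocol set.* The breach description in section 8.9 is open-ended and section 8.4 leaves room for judgement.
- *That a resulting event would automatically count against the device.* Section 13.1 grades relatedness on five levels and section 13.2 separates device-related from other events. Safety is analysed on the Full Analysis Set, so the per-protocol definition would not alter its reporting.
- *That one such patient would decide the non-inferiority result.* The primary endpoint is residual shunt on echocardiography at 6 months (section 7.1.6), and neither condition is itself an occlusion failure. A complication could reach the endpoint through a missing 6-month result imputed as worst case (section 8.9), but that could happen in either arm. The plan also names no method for the confidence interval, so a pass or fail worked out with one particular method shows only that the trial is small.

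**Conclusion.** The point stands as an internal contradiction about who may receive the device. It is firm for thrombus. It is conditional for pulmonary hypertension, because it rests on resistant type being wider than the terms of exclusion (1).

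The documents give no prevalence, so the number of affected patients cannot be derived. If 0 to 2 of the 108 are assumed, that is 0 to 1.9% of enrolment (2/108), and one patient is 1.85% of an arm (1/54). These figures indicate scale only; they are not a predicted effect on the primary result. The case for amending rests on patient safety and uniform screening across centres. It is a change that should be made, and it leaves the sample size, margin and significance level as they are.

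**What to change.** Reconcile contraindications 1 and 2 of section 6 with exclusion criteria (1) and (4) of section 7.1.5.2, using one wording in both places, so that no patient is contraindicated under one section and eligible under the other. Carry that wording to the inclusion and exclusion check at screening (section 7.2). It would also help to state in section 8.9, before database lock, how a contraindicated patient who was nevertheless implanted is treated in the per-protocol set. Which clinical wording is kept is for the sponsor and investigators to decide.

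The cost is a wording amendment to the two lists and the screening form, with ethics approval, and possibly a few lost candidates. An echocardiogram is already scheduled at screening. Whether the agreed pulmonary hypertension wording needs any further assessment depends on the choice made.

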7.1.5.3. Standards and Procedures for the stop of trial/test treatment

Falling off standard:

All the subjects filling out the informed consent and qualified in screening for enrollment into randomized research, when they withdraw from the trial research in any time for any reasons, so long as they failed to accomplish the observation cycle prescribed by the protocol, they shall be deemed as falling off cases, and stop the trial. Common falling off causes include:

- (1) Occurrence of serious adverse events resulted in the furthering completion of the trial;
- (2) Changes in diseases conditions, unsuitable for furthering completion of the trial;
- (3) Loss of follow up;
- (4) The patients or their family members demanding withdrawal from the trial;
- (5) Incapable of furthering completion of the trial for any other reasons;
- (6) The subjects are poor in compliance, influencing the efficacy and safety judgment.

After the subjects' falling off, the researcher must contact the subjects for all possibilities, and ask for the reasons and accomplish all the assessment items possible of completion. When the patients withdraw due to the allergic reaction, adverse reactions, and invalid treatment, the researchers must adopt the corresponding treatment measures according to the actual conditions of the subjects.

Rejecting Criteria:

All the cases already included however comply with any of the following conditions, must be rejected:

- (1) Misdiagnosis (without application of any testing instrument);
- (2) Patients without any testing records (without application of testing instrument);
- (3) Patients incompliance with the inclusion/exclusion criteria (without application of testing instrument);
- (4) Due to the application of any forbidden drug, which results in the incapability for effective evaluation (without application of testing instrument).

For rejection cases it must be explained for the reasons, and their CRF Table must be preserved and ready for review. Without treatment statistical analysis, however after receiving

treatment, with at least one effectiveness and safety records, the patients can participate in the safety analysis according to conditions.

Standards/Procedures for the stop of trial/test treatment:

When adverse events occur, the clinical trial personnel must make clinical judgment in time, and take measures to protect the subjects' rights and interests; when necessary, the ethics commission has the right to terminate the clinical trial; for termination of clinical trial, it should be informed of the subjects, sponsor, ethics commission and SFDA, and explain the reasons.

Before terminating the clinical trial in advance, it should be informed of the medical institutions, ethics commission and SFDA, and explain the reasons.

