8.6 Standard and Reasons for termination of trial based on the statistical

The current trial has no pre-set up middle term analysis and early termination standard correspondingly, therefore, it is inapplicable here. All the statistical analysis shall be carried out after the completion of data gathering, cleaning and final lock up.

8.7 Data statistical method, in combination with missing, unused or wrong data (including withdrawal and termination mid term) as well as the processing method for unreasonable data.

Statistical analysis procedures are implemented strictly according to the Standard Operation Procedure (SOP) by the medical statistical department of National Cardiovascular Disease Center. For details, please refer to relevant documents.

For missing data that may occur during research procedures, during analysis, it shall carry out cutting and transfer targeting at the missing of primary efficacy indices, for the cutting and

transfer method in details, it shall be explained in the prospectus for statistical analysis. In general, it applies single value cutting and transfer method such as LOCF (Last Observation Carry Forward) strategy or WCCF (Worst Case Carry Forward) strategy to carry out processing for the missing data in the primary indices. For the occurrence of missin data in other indices, it would not carry out cutting and transfer, instead it is carried out of analysis for data actually observed.

Wrong and unreasonable data shall be screened during the data screening procedures before statistical analysis. For mid term withdrawn or terminated of the trial, the data of this part of patients shall be included into the final statistical analysis. In the statistical report, it would carry out in detail explanation for the causes of withdrawal or termination patients, for missing data resulted from early stage withdrawal, it should be cutting and transferred according to the missing data processing strategy mentioned above.

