13.2 Countermeasures for adverse events

All adverse events occurring during the research must be recorded in the adverse event table. Investigators shall give targeted treatment and follow-up for adverse events until symptoms disappear or stabilize. Investigators shall make a preliminary judgment on adverse events, and the basic judgment is divided into intraoperative adverse events (any adverse event occurs within 24 hours after the operation), postoperative adverse events, and device-related or non-device-related adverse events.

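### Section 7.1.5.3 lets an implanted subject's participation end because of an SAE, a change in condition or poor compliance, and does not assure that scheduled observation continues.

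*Combined protocol and SAP*

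**What the plan says.** Section 7.1.5.3 defines falling off for randomised subjects who withdraw at any time, for any reason, without completing the observation period: "they shall be deemed as falling off cases, and stop the trial". Three of the six common causes it lists matter here:

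- "Occurrence of serious adverse events resulted in the furthering completion of the trial" (the translation is garbled; it most plausibly means an SAE that prevents completion);
- "Changes in diseases conditions, unsuitable for furthering completion of the trial";
- "The subjects are poor in compliance, influencing the efficacy and safety judgment".

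The paragraph after the list adds a duty once a subject has fallen off: "the researcher must contact the subjects for all possibilities, and ask for the reasons and accomplish all the assessment items possible of completion". For withdrawals due to allergic or adverse reactions or ineffective treatment it adds that "the researchers must adopt the corresponding treatment measures according to the actual conditions of the subjects".

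Section 13.2 governs events already recorded: "Investigators shall give targeted treatment and follow-up for adverse events until symptoms disappear or stabilize".

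The flow chart in section 7.2 schedules ECG, echocardiogram and adverse-event recording at 1, 3 and 6 months. Section 7.1.5.6 adds follow-up to 3 years, without saying whether drop-outs are included.

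On analysis, section 8.7 keeps withdrawn subjects' data. For indices other than the primary one it says: "For the occurrence of missin data in other indices, it would not carry out cutting and transfer". Section 8.9 applies worst-case carry-forward to a missing primary outcome in the full analysis set (FAS), restricts the per-protocol set (PPS) to subjects who finished the trial, and evaluates safety on the FAS.

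**The concern.** In a drug trial, stopping treatment and stopping follow-up are separate decisions. Here treatment is over once the occluder is released. If a subject then stops the trial, what ends is observation of someone who carries the device or has had it removed. Section 7.1.5.3 does not separate the end of participation from the end of observation, and it names adverse outcomes among the reasons for leaving.

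Two things are at stake. First, safety data may be missing for reasons tied to the safety outcome. The protocol's own background (section 4.1) makes late conduction block a central hazard of existing devices: a 3.8% pacemaker rate, with cases even about 4 years after operation. Section 5.1 reports from animal work that the PDO thread starts to degrade at 6 months. Later ECG and echo data therefore bear directly on the claim made for the new device. Second, a 6-month echo that could have been obtained becomes a missing primary outcome.

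**Working it through.** **The two instructions side by side.**

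| Text | What it assures after a subject falls off |
|---|---|
| 7.1.5.3, definition | The subject stops the trial |
| 7.1.5.3, next paragraph | Contact, and whatever assessments can be completed; number and timing not stated |
| 13.2 | Follow-up of the known event until it resolves or stabilises; no scheduled ECG or echo for new or silent events |
| 7.2 flow chart | ECG, echo and adverse-event recording at 1, 3 and 6 months; no statement on drop-outs |
| 7.1.5.6 | Follow-up to 3 years; no statement on drop-outs |

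A site can comply by making one closing assessment, or by completing every remaining visit. On the first reading, a subject who leaves between the 1- and 3-month visits misses 2 of the 3 follow-up visits; one who leaves before month 1 misses all 3, apart from any closing assessment.

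**The plan's drop-out allowance.** Section 8.2.1 inputs: both success rates 0.98, margin 0.08, one-sided alpha 0.025, power 80%, drop-out 10%. With equal rates the formula reduces to

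n = (1.96 + 0.8416)² × 2 × 0.98 × 0.02 / 0.08² = 48.07 per group.

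48.07 / 0.9 = 53.4, rounded up to 54. The stated figure reproduces. The allowance is 0.10 × 54 = 5.4 subjects per group. Section 8.4 makes this a maximum for every cause of exclusion from the main analysis, including ineligibility and non-use of the product. It does not estimate how many would leave after an SAE, a change in condition or poor compliance.

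**Consequence for the primary endpoint (illustration only).** Assumptions: worst-case carry-forward means failure; an unadjusted Wald 95% interval is used (section 8.1.2 specifies a centre-adjusted CMH test but no interval method); 54 are analysed per arm; the counts of imputed failures are mine. At 98% success about one failure per arm is expected (0.02 × 54 = 1.08), so the starting point is 53/54 in each arm.

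Lower limit = (pT − pC) − 1.96 × √[pT(1 − pT)/54 + pC(1 − pC)/54].

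| Imputed failures added | Trial | Control | Difference | Lower limit | Above −8%? |
|---|---|---|---|---|---|
| None | 53/54 | 53/54 | 0.0 | −5.1% | Yes |
| 1 in trial arm | 52/54 | 53/54 | −1.9% | −8.04% | No, narrowly |
| 2 in trial arm | 51/54 | 53/54 | −3.7% | −10.8% | No |
| 1 in control arm | 53/54 | 52/54 | +1.9% | −4.3% | Yes |
| 2 in control arm | 53/54 | 51/54 | +3.7% | −3.4% | Yes |

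One or two missing echoes can matter in a trial of this size. The direction depends on the arm and on whether the subject would have been a success. The one-subject result lies so close to −8% that another interval method could change it.

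**Scoring after removal.** Section 7.1.6 defines 6-month success by the echo finding alone: no residual shunt, or only a minor one. Section 13.4 describes removal of a detached occluder with repair of the defect. If follow-up is kept, a later echo in such a subject could show no shunt and be scored as success. Retaining these subjects therefore also needs a scoring rule.

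**The case against.** The strongest reply is that section 7.1.5.3 is not a removal rule. Its sentence classifies subjects who have already withdrawn, and the list is of common causes, with qualifiers: the change in condition must make completion unsuitable, and the poor compliance must affect the judgment of efficacy and safety. This stands. A reader might infer that any SAE forces exit, or that these subjects simply stop having safety assessments. The text supports neither, since the same section requires contact and completion of possible assessments and section 13.2 adds event follow-up. For a cooperative subject, the scheduled visits are arguably among the assessments that are possible.

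A reader might also infer that adverse-event incidence is understated most in the arm with more early SAEs. That does not follow. Section 8.1.2 describes adverse events by number of cases and occurrence, so a subject who leaves after an SAE is already counted for it. Only later, different events can be lost. Not imputing missing safety data is ordinary practice and no defect in itself. Nor do the documents give any figure showing that these subjects are at highest risk.

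What the reply does not remove is the ambiguity. Possible assessments can be read as one closing visit, event-driven follow-up is not a schedule, and keeping withdrawn subjects' data does not supply data never collected.

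**Conclusion.** The concern holds in a limited form. The plan permits participation to end for these three reasons, does not separate that from the end of observation, and leaves two instructions in one section unreconciled. A site following the text may stop observing an implanted subject who could still be reached. That subject stays in the FAS safety denominator, has a worst-case primary outcome in the FAS, and leaves the PPS.

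No size or direction of bias can be derived from the documents. The table of limits shows sensitivity under stated assumptions and is not a forecast. The conclusion assumes that worst-case carry-forward means failure; the plan does not define the term, and if it meant the worst value already observed, a subject with good earlier echoes would not be scored as a failure. The safety part and the PPS exclusion do not depend on that assumption. This is a cheap improvement that goes beyond tidying the wording.

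**What to change.** State in sections 7.1.5.3 and 13.2 that an SAE, a change in condition, poor compliance, or occluder removal or re-intervention does not by itself end scheduled data collection. Such subjects keep the 1-, 3- and 6-month ECG, echo and adverse-event assessments and the follow-up of section 7.1.5.6, unless they withdraw consent, are lost to follow-up or die. This says what the duty to complete possible assessments means, and so reconciles it with the instruction to stop the trial. Section 7.1.5.6 should say that these subjects are included.

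Add to section 7.1.6 that a subject whose occluder was removed or who had re-intervention counts as a failure for the primary endpoint, whatever the later echo shows.

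The change concerns data collection and endpoint scoring only; clinical care is untouched. The visits are already planned for every subject, so the cost is the wording and some effort to retain subjects after an adverse outcome.
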